To guard against bias, children are randomly assigned to condition. A randomization scheme was pre-allocated at the beginning of the study by [name] at CRESP and uploaded to RedCap using a blinded allocation module. Allocation is requestable as children qualify for the study from CRESP. This ensures that the assessor at pre-test is blind to allocation. To ensure approximately equal allocation to each condition at each site, separate randomization schemes are used for each site. Flow through the study and drop outs at each phase are tracked following EQUATOR reporting guidelines.

Data Reduction

Estimated Dose

We compute estimated dose provided as follows:

$$\text{Dose} = \text{number of sessions reported by families} * \text{percent sessions documented based on recordings} * \text{recasts/sentences read verbatim observed in transcribed sessions}$$

Production Data

The dependent variable is production accuracy scored item by item as correct (1), incorrect (0), or unscorable (missing). Individual items are additionally coded as the syntactic type elicited (passive voice or object relative clause) and as treated/untreated clause type since that is counterbalanced across participants.

Eye-tracking Data

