Second, for each time window (early and late), we will assess the extent to which Treatment Condition affects interpretation of the treated noncanonical structure. Our dependent variable will be **Structural Sensitivity**, calculated as *an averaged difference score of Agent Preference in the canonical structure (SRC, active) minus the noncanonical structure for each structure (ORC, passive) for each child.* This measure is selected rather than Agent Preference because it captures the **degree to which a child differentiates the two structures** from each other. Sensitivity to passive/object relative clause cues will be evident in values greater than 0, with higher values mapping onto increased sensitivity. Each child will receive a single Structural Sensitivity score for active/passives and a single Structural Sensitivity score for subject/object relative clauses at each test point.

Analytic Approach

For both comprehension and production outcomes, we utilize generalized linear mixed models to examine change over time for each condition. The adoption of generalized linear mixed models (GLMM) with random effects for subjects and items as the statistical approach has advantages in that we do not need to exclude children for failing to produce scorable responses given that this model can account for uneven response rates across children (Baayen, Davidson, & Bates, 2008) and it accounts for item level variance that can affect results.

Production probe accuracy will be analyzed with a logit link function. Use of a logit link function for production data also closely mirrors the underlying data structure in which individual items are scored as correct or incorrect. Structural sensitivity will be analyzed with linear mixed-effects models. Maximal models will include random intercepts (and possibly random slopes) for subjects, items, and clause type (Barr, Levy, Scheepers, & Tily, 2013), and parameter-specific p-values will be estimated with degrees of freedom determined through Satterthwaite approximation (Luke, 2017).

We will model comprehension and production outcomes separately, though we make similar predictions as to the effect of treatment on each outcome measure. Prior to carrying out the main analyses, we will check for differences attributable to participant sex and race (relevant biological variables). These will be included in future analyses if necessary, but prior work suggests that they are not likely to influence outcomes.

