In the somewhat likely event that the interaction between time point and treatment is not significant, we can directly test for treatment efficacy by comparing the effect of treatment on the treated vs. untreated structures. We expect that the model estimate for Treated or Untreated clause will be significant at p<0.05 level, favoring the treated clauses, demonstrating that treatment was effective and ruling out maturational effects.

$$\begin{aligned} \text{Likelihood of a Correct Production} &= \text{TestPoint} * \text{TreatedOrUntreated} \\ &\quad + (1|\text{item}) + (\text{clause type} |\text{subject}) \\ \text{Structural Sensitivity} &= \text{TestPoint} * \text{TreatedOrUntreated} \\ &\quad + (\text{clause type} |\text{subject}) \end{aligned}$$

Aim 2. Determine whether the influence of delivery method (illustrated syntax stories or recast therapy) on dose delivered (number of exposures to the target) is of sufficient magnitude that changes in child outcomes are observed when treatment is delivered by caregivers.

We will first determine whether dose differs across the two at-home conditions. We will carry out an unpaired two-tailed t-test comparing the estimated dose delivered for each condition. We anticipate that the two conditions will differ and that the distributions will show low degrees of overlap (p<.05, d>.5).

To test the key question in Aim 2, we will test for a dose by test point or dose by treatment condition by test point interaction for stories at home and recasts at home conditions. Well-matched groups at pretest will be evident if the two conditions do not differ at pre-test. If one treatment condition is more effective than the other, this should be evidenced by an interaction between test point and treatment contrast effects that are significant at the p<.05 level; if, as we hypothesize, dose is a critical component of this difference, a two- or three-way interaction between time and dose or between time, treatment and dose will be observed. We would interpret the two-way interaction as indicating that dose, rather than treatment is critical for obtaining the key outcomes. A three- way interaction suggests that the delivery method modifies the effectiveness of the total dose.

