$$\begin{aligned} \text{Likelihood of a Correct Production} &= \text{TestPoint} * \text{TreatmentCondition} * \text{EstimatedDose} \\ &\quad + (1|\text{item}) + (\text{clause type} |\text{subject}) \\ \text{Structural Sensitivity} &= \text{TestPoint} * \text{TreatmentCondition} * \text{EstimatedDose} \\ &\quad + (\text{clause type} |\text{subject}) \end{aligned}$$

In the event that the interaction between time point and treatment is not significant, we can directly test for treatment efficacy by comparing the effect of treatment on the treated or untreated structures. We expect that the model estimate for Treated vs. Untreated clause will be significant at p<0.05 level, favoring the treated clauses, demonstrating that treatment was effective and ruling out maturational effects.

$$\begin{aligned} \text{Likelihood of a Correct Production} &= \text{TestPoint} * \text{TreatedOrUntreated} \\ &\quad + (1|\text{item}) + (\text{clause type} |\text{subject}) \\ \text{Structural Sensitivity} &= \text{TestPoint} * \text{TreatedOrUntreated} \\ &\quad + (\text{clause type} |\text{subject}) \end{aligned}$$

Power Analysis for Production

Power analyses were carried out using Monte Carlo simulation (5,000 iterations) via SAS 9.4 and PROC GLIMMIX using residual pseudolikelihood estimation of a binary logistic mixed effects model with item responses (n=20) nested within tests (n=4 representing test point and clause type repeated measures) that are nested within children (n=120) who have been randomly assigned to treatment conditions, counterbalanced across the 2 clauses. Random effects are included for items within clauses, as well as four correlated child-level random effects (i.e., for each of the four repeated measures). A single model was used to estimate power in alignment with the overall design of the study in which children are randomly assigned to one of FOUR conditions. Power for the more focused models described above can be inferred from the power estimates for the treatment contrasts below. By adopting this randomization scheme and model design, we retain the ability to test unplanned contrasts that go beyond the planned analyses for the Aims if we so chose (e.g., recasts in the lab vs. recasts at home) in order to carry out secondary analysis associated with cost effectiveness, dose, or home environment.

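### Clause type is coded and counterbalanced but has no fixed effect in any Aim 1 or Aim 2 equation; the cost is modest precision for Structural Sensitivity and bias only if counterbalancing is materially lost

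*Protocol*

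**What the plan says.** Under Data Reduction (Production Data), each item is "coded as the syntactic type elicited (passive voice or object relative clause) and as treated/untreated clause type since that is counterbalanced across participants". Power Analysis for Production repeats the design feature: children are "randomly assigned to treatment conditions, counterbalanced across the 2 clauses". Clause type is therefore a two-level design factor that is already in the data.

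The protocol then handles it in two ways:

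- The Analytic Approach prose lists it as a random factor: "Maximal models will include random intercepts (and possibly random slopes) for subjects, items, and clause type".
- Every equation under Aim 1 and Aim 2 has it as a by-child slope, typeset as "clause type} |\text{subject". The production equations add a random intercept for item.

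The fixed parts are TestPoint by TreatmentCondition, TestPoint by TreatmentCondition by EstimatedDose, and TestPoint by TreatedOrUntreated. None contains clause type or its interaction with TestPoint. The power model does not name a fixed clause effect either: "Random effects are included for items within clauses, as well as four correlated child-level random effects". Its simulated scores use one pretest distribution for both clauses and do not separate the clauses at posttest.

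**The concern.** Passives and object relatives need not improve at the same rate. A by-child clause slope with no matching fixed effect assumes that the average clause difference is zero. It also has no time component, so a difference in gain (ClauseType x TestPoint) falls in no term of the model.

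Two things are at stake. In the linear model the unmodelled gap goes into the residual variance and widens the reported standard errors of the interactions on which both aims rest. In either model, only the balance of treated clause across children keeps the gap out of the treated-versus-untreated estimate.

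The prose adds a smaller problem. A variance for a two-level grouping factor rests on one degree of freedom and cannot be estimated usefully, and the equations do not specify such a term. Prose and equations should agree.

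**Working it through.** **1. The plan's own figure.** Power Analysis for Production gives .61 for parent recasts. I read this as the within-child contrast, treated gain minus untreated gain, with 120/4 = 30 children and two-sided alpha .05.

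- Treated gain variance: 4.0² + 2.5² − 2(.90)(4.0)(2.5) = 4.25.
- Untreated gain variance: 2.5² + 2.5² − 2(.90)(2.5)(2.5) = 1.25.
- SD = √5.5 = 2.345; mean difference 1.0; paired t-test power .617.

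This agrees with .61. The match is to the untruncated moments: drawing rounded and truncated scores as described and applying a t-test gave .83. The figure contains no clause gap.

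**2. Structural Sensitivity (linear), balanced clauses.** Assumed: 60 children (two arms of 30), two clauses, two test points, residual SD .12, child-intercept SD .10, clause-slope SD .08. The total SD is √(.10² + .04² + .12²) = .161, close to the .17 in Power Analysis for Eye Tracking.

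With the by-child intercept and clause slope fitted, each child leaves two within-child degrees of freedom. A gap g in gain adds (g/4)² per cell over four cells, that is g²/4 per child, or g²/8 to the residual variance. So:

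- SE of TestPoint x TreatedOrUntreated = √(4σ²/60); the SE factor is √(1 + g²/(8σ²)).
- g = 0: √(4 × .0144/60) = .0310, factor 1.00.
- g = .1: factor √(1 + .00125/.0144) = 1.04.
- g = .2: √(4 × .0194/60) = .0360, factor √(1 + .005/.0144) = 1.16.

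Fitting the mixed model to simulated data (25 runs per setting) gives:

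| Gap in gain | SE as written | SE with clause main effect | SE with ClauseType x TestPoint |
|---|---|---|---|
| 0 | .0308 | .0308 | .0308 |
| .1 | .0316 | .0316 | .0304 |
| .2 | .0361 | .0356 | .0311 |

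At .2, residual variance is .0197 as written and .0146 with the interaction. A separate fit at a gap of .2 gave .0352 against .0304 for TestPoint x TreatedOrUntreated, and .0364 against .0317 for TestPoint x TreatmentCondition. The ratios are 1.16, 1.16 and 1.15. Point estimates differed by less than .001 between models, so under balance the fault is an overstated SE, not a shifted estimate.

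A static clause difference of .2 left the interaction SE unchanged (.0305). It raised the SE of the TreatedOrUntreated main effect from .0188 to .0322, which is why the main effect is worth adding too.

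**3. Production (logit).** Simplified simulation: 60 children, 20 items per test, no item effect, assumed values, true interaction .45 logits, 40 runs per setting.

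- 30/30 split, 1-logit gap: mean z 2.50 as written, 2.56 with the fixed terms.
- 24/36 split, .5-logit gap: mean estimate .34 as written, .45 with the terms.
- 24/36 split, 1-logit gap: .20 as written, .41 with the terms; mean z 1.25 against 2.45.

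**4. Size of the bias.** On treated-minus-untreated gain, bias ≈ gap × (difference in clause counts)/n.

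- 18/17: gap × 1/35 = .029 × gap.
- 24/36: gap × 12/60 = .20 × gap. For a linear gap of .2 this is .04, and the fitted linear model shifted by about .04.
- Attrition bound: two arms enrol 2 × 160/4 = 80 children, 40 per clause if exactly balanced. If all of a 15% loss (12 children) fell on one clause, the split is 28/40 and the bias 12/68 = .18 × gap.

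**The case against.** The best defence is that counterbalancing already protects validity, that no clause gap in gain is documented, and that (1|item) and the by-child slope largely absorb a static clause difference in the production model. All of that stands. A gap of .2 is also large: it is about two thirds of the .29 difference between typically developing children and children with DLD in the preliminary data (.2/.29 = .69).

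Three stronger readings are tempting, and the document does not support them.

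- *The stated production powers are too high.* A reader might add the squared gap to the raw-score variance of 5.5 and take .617 down to .547 at one point or .405 at two, or discount the stated .75 and the 80% threshold in the same way. That is linear arithmetic. The production model is logit, with no free residual variance and no by-child TestPoint slope. A further small fit at a 1-logit gap gave interaction SEs of .153 against .153–.154 and .154 against .155–.156, without and with the terms. The planning SDs come from a previous study and may already contain clause differences; the terms would then add to power.
- *Thirty-five per arm forces bias.* An odd arm gives 18/17, which is trivial.
- *A random slope across clause types could leave an effect untestable on one degree of freedom.* That model is only a possibility in the prose; no Aim equation uses clause type as a grouping factor.

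**Conclusion.** The point holds as a specification fault of modest size. The equations omit a two-level design factor from the fixed part, and the prose gives it a random role that the equations do not.

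For Structural Sensitivity, the reported SEs of the TestPoint interactions are about 15% too large at an assumed gap of .2, about 4% at .1, and unaffected at zero, given a residual SD of .12. For production under exact counterbalancing the loss is negligible. In both models the treated-versus-untreated effect is biased by the gap times the proportional imbalance in treated clause. That matters only for a material imbalance, and the 24/36 illustration is slightly beyond what one-sided attrition alone would produce from exact balance.

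The production results rest on small simplified simulations with assumed values. Nothing here overturns the stated power figures or the validity of a balanced comparison.

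**What to change.** - Add ClauseType and ClauseType x TestPoint as fixed effects to every Aim 1 and Aim 2 equation, for both outcomes. The main effect alone barely helps the interaction tests.
- In the Analytic Approach, delete clause type from the list of random grouping factors so that prose and equations agree.
- Keep the by-child clause slope only where both clauses are in the data. In a model restricted to the treated structure each child has one clause, and the slope cannot be identified.

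The cost is two fixed parameters per model and some wording. Clause type is already coded, so no new data are needed, and precision was not lost when the gap was zero.

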We will also use generalized additive mixed models (GAMMs) to model longitudinal patterns in eyetracking data (i.e., looks to the agent) to examine and visualize timing of stimulus effects and changes in focus at key points during and after presentation of the prompt. GAMMs model fixations as an intensive time series (Cho et al., 2018, 2022) and allow identification of key points of separation. Moreover, the GAMMs models do not require prespecification of windows of time, providing more flexibility and sensitivity when modeling differences in eyetracking over time and between groups. The specification of the GAMMs models will mirror the GLMM equations below, except that smoothing functions will be used for an additional TIME predictor to fit a spline regression for each time series.

Aim 1. Determine the relative differences in the efficacy of illustrated syntax stories and recast therapy when treatment is dose controlled and delivered by highly trained SLPs in the laboratory.

We will first confirm that we achieved control of dose in the two in-lab conditions. We will carry out an unpaired two-tailed t-test comparing the estimated dose delivered for each condition. We anticipate that the two conditions will not differ and that the distributions will show high degrees of overlap ($p>.5$, $d<.3$).

To test the key question in Aim 1, we will compare the relative effect of treatment condition by testing for differences between the treatment effect estimates of stories in the lab and recasts in the lab conditions.

Well-matched groups at pretest will be evident if the two conditions do not differ at pre-test. If one treatment condition is more effective than the other, this should be evidenced by an interaction between test point and treatment contrast effects that are significant at the p<.05 level; if, as we hypothesize, the two conditions are equally effective there will be no significant interaction between test point and treatment. We are powered to detect an effect size difference of .35 (2 raw score points) or larger on production.

$$\begin{aligned} \text{Likelihood of a Correct Production} &= \text{TestPoint} * \text{TreatmentCondition} \\ &\quad + (1|\text{item}) + (\text{clause type} |\text{subject}) \\ \text{Structural Sensitivity} &= \text{TestPoint} * \text{TreatmentCondition} \\ &\quad + (\text{clause type} |\text{subject}) \end{aligned}$$

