The influence of dose (Aim 2) was simulated by predicting different dose distributions for each condition. These distributions were simulated and then we randomly sampled from the distribution for each case. Hypothesized distributions of dose lead to substantial changes in the result, and thus we make our method of construction these distributions clear here. We assume that a minimum dose is achieved during the training visits (home condition) or by attending at least 1 session (lab condition) for all children. The two in-lab conditions are highly similar and both assume that 25% of participants attend between 1 and 12 sessions, 25% attend between 12 and 16, and the remainder have perfect attendance. This is a conservative estimate based on attendance data from our summer camp study.

The two at-home conditions require slightly more explanation. We assume for recasts that the first quartile has a dose of up to 1 recast/5 min for 60 min per week. The next quartile extends up to 1 recast/5 min for 120 min per week. The third quartile ranges up to a dose of 1 recast every 3 min for 120 min per week and the last quartile assumes target delivery. Similarly, syntax stories at home escalates from reading 1x/week to reading 2x/week to reading 4x/week (as asked) to reading 1 syntax story daily as the maximum. Several families in the pilot data for the syntax stories read the provided syntax stories daily.

Table 1. Hypothesized dose delivered by condition, in quartiles

	Recasts in lab	Stories in lab	Recasts at home	Stories at home
minimum	60	60	60	60
1st quartile	768	768	96	240
median	912	930	192	460
3rd quartile	960	960	320	960
maximum	1008	960	960	1680

Next the gain obtained from each dose was estimated by multiplying the dose provided by a value drawn from a uniform distribution ranging from .0005 to .006, to account for the fact that some children will be more responsive to any given dose than others. Finally, the gain was added to the pretest scores to yield posttest values. Simulations were checked to ensure that final post-test means and standard deviations for the treated structure were in line with estimates for post-test gains used for Aim 1 simulations. Planned statistical analysis were carried out over the simulated data and these simulations were repeated 1000 times.

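### The written formulas give children no test-point effect of their own, unlike the power model, so the Aim 1 production test exceeds 5% if true gains vary between children

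*Protocol*

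**What the plan says.** The general statement in the Protocol, Analytic Approach, is: "Maximal models will include random intercepts (and possibly random slopes) for subjects, items, and clause type". Slopes are optional there, and TestPoint is not named.

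The formulas under Aim 1 and Aim 2, including the fallback models for treated versus untreated structures, are explicit. For production the random part is `(1 | item) + (clause type | subject)`. For Structural Sensitivity it is `(clause type | subject)`. In both, a child has an intercept and a clause-type difference, and nothing else.

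Under Aim 1 the deciding evidence is "an interaction between test point and treatment contrast effects that are significant at the p<.05 level".

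Power Analysis for Production describes a different model. Its data are "item responses (n=20) nested within tests (n=4 representing test point and clause type repeated measures) that are nested within children (n=120", and it includes "four correlated child-level random effects (i.e., for each of the four repeated measures". It then states: "Power for the more focused models described above can be inferred from the power estimates for the treatment contrasts below". In the dose simulation of the same section, gain per exposure is drawn from .0005 to .006 because "some children will be more responsive to any given dose than others".

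**The concern.** Four child effects, one per test point and clause type, let each child have its own change from pre-test to post-test. An intercept and a clause-type effect do not. Under the written formulas, a child's 20 post-test items on a clause are independent evidence about change once those two effects are known. If children truly differ in gain, that variation is left out of the standard error of TestPoint by treatment, which becomes too small.

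Two things are at stake. The Aim 1 comparison of lab recasts with lab stories could be declared different more often than the stated 5% allows. And the power quoted for the planned models comes from another covariance structure. Because slopes are only optional in the text, the term that sets the p-value could also be added or left out after the data are seen.

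**Working it through.** **Inputs from the Protocol.** 35 children expected per condition (Human Subjects section); 120 children, so 30 per condition, in the power analysis; 20 items per test; 2 clause types by 2 test points. Pre-test M 3.0, SD 2.5, range 0 to 7. Treated post-test: lab recasts 8.0 (SD 3.5), lab stories 6.0 (3.5), home stories 5.5 (4.0), parent recasts 4.0 (4.0). Pre-post correlation .90.

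**Not given, so assumed.** The child-level SD of change in logits (0 to 1.0 tried); the correlation of a child's two clause changes (-.3 to .7 reported); a two-sided test.

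**1. The stated power.** Change SD = √(2.5² + s² − 2·.90·2.5·s), which is √2.75 = 1.66 for s = 3.5, √4.25 = 2.06 for s = 4.0, and √1.25 = 1.12 for the untreated clause (s = 2.5). Power = Φ(d/√((s₁² + s₂²)/30) − 1.96), with s₁ and s₂ the change SDs. For home stories against parent recasts, 1.5/√(8.5/30) = 2.82, so power is Φ(0.86) = .80. A simulation (300 trials, four correlated child effects, clauses independent, no item effects) is set beside it:

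| Comparison | Stated | Closed form | Simulated |
|---|---|---|---|
| Parent recasts, main effect | .61 | .65 | .69 |
| Home stories vs parent recasts | .75 | .80 | .50 |
| Parent recasts vs lab stories | .90 | .985 | .74 |
| Parent recasts vs lab recasts | .99 | >.99 | 1.00 |
| 2-point difference (simulated: lab recasts vs lab stories) | .80 | not used | .79 |

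The main effects stated as above .95 also reproduce. The .61, .75 and .90 do not, but the correlation between clauses and the item variance are not given. That mismatch has no bearing on this point.

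**2. Type I error of the Aim 1 production test.** Null simulation, 35 against 35, two clauses by two test points by 20 items, 600 trials per setting. Monte Carlo error is about 1 point, or 2 points near 30%. Both clauses are fitted with the written child structure; item effects are omitted. The logit settings use a baseline of −1.7, child SD 1.0, clause SD 0.5, and a treated gain of 0.9 in both arms.

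| True variation in change | As written | With by-child TestPoint slope |
|---|---|---|
| None | 4.8% | 3.8% |
| Protocol scores as true scores, M 8 | 7.5% | 4.0% |
| Protocol scores as true scores, M 6 | 8.7% | not run |
| Shared SD 0.3 logit | 8.5% | not run |
| Shared SD 0.5 | 12.8% | 5.2% |
| Shared SD 0.7 | 22.3% | not run |
| Shared SD 1.0 | 30.3% | not run |
| Treated clause only, SD 0.5 | 9.7% | not run |
| Treated clause only, SD 1.0 | 15.8% | not run |
| Protocol scores as observed scores, r = .90, M 8 | 0.2% | 0.2% |

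**3. The last row.** Binomial noise in a 20-item change score is at most about √(3·17/20 + 8·12/20) = √7.35 = 2.7 points, and the literal change SD of 1.66 lies below it. KR-21 reliability is (20/19)(1 − M(20 − M)/(20·SD²)): .62 at pre-test, .64 at M 8 and .69 at M 6. With such reliabilities the observed correlation would be capped near √(.62·.64) = .63 to √(.62·.69) = .65. KR-21 assumes equally difficult items. An observed correlation of .90 is therefore hard to produce with independent binary items.

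**4. Structural Sensitivity.** Each child has four scores. In balanced data the written model pools the variance of the sum and the difference of the two clause changes, (1 + ρ) and (1 − ρ), while the test depends on the sum. The variance is understated by a factor 1 + ρ, so type I error = 2(1 − Φ(1.96/√(1 + ρ))). This gives 1.9% at ρ = −.3, 3.9% at −.1, 5.0% at 0, 7.4% at .2, 8.6% at .3, 11.0% at .5 and 13.3% at .7.

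**The case against.** The strongest reply is that the size is unknown. The plan gives no child-level SD of change, and its simulations work with whole test scores, not with true scores plus item sampling. Taken literally, those scores give a rejection rate far below 5%. This stands as to size: a reader might infer that the test simply runs at about twice its level, and the document does not support any such fixed figure. It does not remove the defect, because the literal reading needs score reliability that a 20-item binary probe with these means and SDs could hardly reach.

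A reader might also extend the figures to Aim 2. Its key tests are interactions with dose, the dose term absorbs part of the variation in gain, and no error rate was computed for them. Nor can Structural Sensitivity be called inflated in general: at zero or negative correlation it is not.

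The allowance for random slopes is a fair point, since the repair is compatible with it. But the sentence does not name TestPoint, and none of the formulas uses it.

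The power section is open about using one four-condition model and inferring the rest. That explains the different fixed effects. It does not explain why the child effects differ.

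Finally, the plan expects no interaction in Aim 1, so inflation works against the investigators' own hypothesis. That lessens any suspicion of bias in their favour, but a false difference between the treatments would still be a wrong answer to the key question.

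**Conclusion.** The concern holds in conditional form. That the formulas omit a by-child TestPoint effect, and that the power model contains one, can be read directly from the Protocol. The consequence for Aim 1 production depends on how much true gains vary: near 5% if they do not, about 7.5 to 9% with the protocol's scores read as true scores, about 8.5 to 13% for a shared change SD of 0.3 to 0.5 logit, and about 30% at 1 logit. The plan's own dose simulation assumes that gains do vary. The figures rest on both clauses entering the model and on no item effects.

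For Aim 2 and for the treated-versus-untreated fallback models the omission is the same and its effect is not quantified. For Structural Sensitivity, error is inflated only under a positive correlation between a child's two clause changes, for example 8.6% at .3.

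**What to change.** In the production formulas, replace `(clause type | subject)` with child random effects for each test point by clause type, as in the power model. At minimum, add a by-child TestPoint slope. State that this term is kept in any simplification after non-convergence. For Structural Sensitivity, add `(1 | subject:TestPoint)` or use an unstructured covariance over the four scores. Make the general sentence on random effects name TestPoint. If the present formulas are kept instead, power should be re-run under them, but that would leave the type I error as it is.

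The cost is an edit to the formulas and somewhat wider standard errors for change. By normal approximation, the rejection rates imply standard errors short by a factor of 1.96/1.78 = 1.10 at 7.5%, 1.96/1.71 = 1.15 at 8.7% and 1.96/1.52 = 1.29 at 12.8%. In the settings with varying gains where the slope was fitted, it brought the rate to 4.0% (from 7.5%) and 5.2% (from 12.8%). No new data are needed.
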